2.4.5 Analysis of Safety Endpoints

Safety analyses will be provided by chronic, flare-up dosing and overall, unless otherwise specified.

General Rules

All safety analyses will be performed on the safety populations defined in [Section 2.3](#), unless otherwise specified, using the following rules:

- The baseline value when summarizing overall visits is defined as the last available value prior to the first chronic dose of study drug.
- The baseline value when summarizing over flare-up visits only is defined as the last available value prior to or on the date of first dose of flare-up treatment within the particular cycle. For the NHS study, the baseline value when summarizing over flare-up visits is defined as the value on the Day 1 visit of the corresponding flare-up.
- The potentially clinically significant (PCS) values for pre specified lab, vital sign and ECG variables are values according to predefined criteria/thresholds (see [Appendix 6.2](#)).
- For AEs, the following conventions for partial or completely missing date imputations will be implemented:

- If the start date is completely missing, the start date is imputed as the date of first dose and the AE is considered treatment emergent and assigned to the chronic dosing period.
- If the day and month of the start date are missing and the start year is the same as the year of first dose, the start date is imputed as the date of first dose and the AE is considered treatment emergent and assigned to the chronic dosing period. If the start year is prior to the year of first dose, the start date is imputed as January 1 of the year and the AE is not considered treatment emergent.
- If the day of the start date is missing and the start month and year is within a period of time within a flare-up treatment, the start date is imputed as the date of the flare-up treatment in the same month as the AE, and the AE is considered treatment emergent and assigned to the flare-up dosing period. Otherwise, if the day of the start date is missing and the start month and year is on or after the date of first dose, the start date is imputed as the date of first dose or the first day of the month of the AE, whichever is later, and the AE is considered treatment emergent and assigned to the chronic dosing period. Otherwise, if the start month and year is before the month and year of first dose, then the start date is imputed as the first day of the month of the AE, and the AE is not treatment emergent.
- Partial AE end dates will be imputed as the last day of the month or year for missing end dates. Completely missing end dates will be imputed as the date of last known treatment exposure for the subject.
- For concomitant medications, the following conventions for partial or completely missing date imputations will be implemented:
 - If the start date and end date are completely missing, then the start date is imputed as the date of informed consent, the end date is the date of last assessment for the subject, and the concomitant medication would be considered both prior and concomitant and assigned to both the chronic dosing period and flare-up period (if applicable to the subject).
 - Partial start dates are imputed as the first day of the month (if only missing the day) or January 1 (if missing day and month), and partial end dates are imputed as the last day of the month (if missing the day only), or December 31 (if missing the day and month). Prior Medications would then be defined as any medications that started prior to the date of first dose. Concomitant medications for chronic dosing would be defined as medications taken at any point in time during the chronic treatment period. Concomitant medications for flare-up dosing would be defined as medications taken at any point in time during any flare up cycle, per imputed or non-imputed dates.
 - Lab data identified as having a “Flare X” visit name will be assigned to a flare-up cycle based on the date of the lab data and the visit date window as in the following algorithm:

- If an observation has a designation of “Flare X” for the visit, then the date of the observation will be compared to the dates of dosing for flare-up cycles and weeks.
- If the observation falls within 14 days of a known flare-up dose cycle and week date, then it is assigned to that particular flare-up cycle and week.

Summaries of WBCT, C-SSRS (suicide ideation/behaviour), laboratory data, vital signs, linear/knee height, weight/BMI, electrocardiograms, and prior/concomitant medications will include the NHS data, where applicable.

Analyses of Adverse Events

The primary focus of AE summaries will be on TEAEs in the treatment period. Pre-treatment and post-treatment AEs will be described separately.

Adverse event incidence tables by SOC and PT will be sorted by decreasing frequency incidence of SOC and by decreasing incidence of PT within SOC. The number (n) and percentage (%) of subjects experiencing an AE will be presented by treatment (chronic dosing, flare-up dosing and total palovarotene [overall]). Multiple occurrences of the same event in the same subject will be counted only once. The denominator for computation of percentages is the safety population for the chronic dosing and overall group and the number of subjects in the safety population with flare-up dosing for the flare-up dosing group. TEAEs by Pediatric Subjects (<18 years) and Adult Subjects (≥18 years) are summarized

The following TEAE summaries will be generated for the safety populations:

Analysis of Treatment-Emergent Adverse Events

- Overview of TEAEs, summarizing number (%) of subjects with
 - TEAEs
 - TEAEs possibly related to treatment
 - TEAEs by maximal severity
 - Treatment-emergent SAEs
 - Treatment-emergent SAEs possibly related to treatment
 - TEAEs leading to dose modification or interruption of study drug
 - TEAEs leading to permanent study drug and study discontinuation
 - TEAEs leading to death
- All TEAEs by primary SOC and PT, showing number (%) of subjects with at least one TEAE
- All TEAEs with incidence $\geq 5\%$ in the overall group by primary SOC and PT.
- All TEAEs by maximal severity, presented by primary SOC and PT, showing number (%) of subjects with at least one TEAE by severity (i.e., mild, moderate or severe)
- All TEAEs by relationship, presented by primary SOC and PT, showing number (%) of subjects with at least one TEAE by relationship (i.e., not related, at least possibly related)

- All TEAEs leading to Dose Modification of Study Drug
- All TEAEs leading to Dose Interruption
- All TEAEs leading to Permanent Discontinuation of Study Drug
- All TEAEs leading to Study Discontinuation

Analyses of Pre-Treatment AEs

- All pre-treatment AEs by primary SOC and PT, showing number (%) of subjects with at least one pre-treatment AE

Analyses of Post-Treatment AEs

- All post-treatment AEs by primary SOC and PT, showing number (%) of subjects with at least one post-treatment AE
 - Post-treatment SAEs
 - Post-treatment SAEs possibly related to treatment
 - Post-treatment AEs by maximal severity
 - Post-treatment AEs leading to permanent study drug and study discontinuation
 - Post-treatment AEs leading to death

Listing will be provided for all pre-treatment AEs, all TEAEs, all SAEs, all TEAEs leading to dose modification or interruption of study drug, all TEAEs leading to permanent study drug discontinuation, all deaths, and all post-treatment AE categories noted above.

Analyses of Laboratory Variables

The summary statistics of all laboratory variables, including raw values and changes from baseline, will be calculated for each visit. Central lab values will be summarized; if local labs exist but no central labs are available, then local labs will be summarized. Summary tables will be provided for all treatment visits, both chronic and flare-up visits. For these tables, the baseline value for the MOVE trial is the last available value prior to or on the date of first dose of chronic treatment. For the NHS study, the baseline value is the value taken at the Day 1 visit.

Summary tables will also be provided for flare-up treatment visits only using date of flare-up dosing to derive change from baseline. For flare-up treatment, subjects may contribute more than one observation for summaries due to multiple cycles of flare-up treatment. Each cycle of flare-up treatment will be summarized separately. For these tables, the baseline value for the MOVE trial is the last available value prior to or on the date of first dose of flare-up treatment within the cycle. For the NHS study, the baseline value is taken at Day 1 of each individual flare-up. In addition, for all laboratory parameters, the mean and mean change from baseline at all chronic visits and all flare-up cycle safety visits will be plotted separately.

The incidence of potentially clinically significant (PCSs) at any time (see Appendix 6.2 for the criteria defining potentially clinically significant (PCS) for clinical laboratory parameters) during

the treatment period will be summarized. One summary table will be presented for all chronic visits (non-flare-up visits in the NHS) and for flare-up treatment visits. For derivation purposes for chronic visits, the baseline value for the MOVE trial is the last available value prior to or on the date of first dose of chronic treatment. For the NHS study, the baseline value is the value taken on the Day 1 visit. For flare-up summaries, the baseline value for the MOVE trial is the last available value prior to or on the date of first dose of flare-up treatment with the cycle. For the NHS study, the baseline value is the value taken on the Day 1 visit of the corresponding cycle.

A focus will be on new-onset PCS values, i.e., subjects with pre-existing PCS values at baseline will not be considered to have new onset values after start of study drug. Pre-treatment was defined as the last value prior to initiation of chronic treatment. For flare-up treatment, PCS will be summarized at the subject-level and the flare-up level. Flare-up analyses may include subjects multiple times as a subject may have more than one flare-up treatment cycle within the study, whereas the subject-level analyses will include each subject once, summarizing at least one post-baseline PCS abnormality across all flare-up cycles.

All PCS values will be presented in a subject-based separate listing as well including baseline values, PCS values and follow-up values.

Pregnancy test results for females of child-bearing potential were provided as subject listings.

Analyses of ECG Variables

The summary statistics of all ECG variables (ECG values and changes from baseline) will be calculated for each visit. Mean heart rate, RR, PR, QRS, QT, QTcF, and QTcB will be determined using centralized readings.

Absolute QTc interval prolongation QTcF, and QTcB will be summarized at baseline and post-baseline, using counts of subjects and the following criteria:

- QTc interval >450 msec
- QTc interval >480 msec
- QTc interval >500 msec
- QTc interval increases from baseline >30 msec
- QTc interval increases from baseline >60 msec

The incidence of ECG abnormalities at any time (see [Section 0](#) for the abnormality list) during the treatment period will be summarized by visit and category (rhythm, conduction, morphology/chamber enlargement, axis deviation, myocardial infarction, ST Segment/T waves/U waves).

New onset ECG PCS values will be summarized for chronic treatment visits. Subjects with pre-existing ECG PCS values at baseline will not be considered to have new onset values after start of study drug. PCS will be summarized at the subject-level. For flare-up treatment, PCS will be summarized at the subject-level. The PCS list is provided in [Appendix 6.2](#).

All PCS values will be presented in a subject-based separate listing as well including baseline values, PCS values and follow-up values.

All ECG abnormalities (rhythm, conduction, morphology/chamber enlargement, axis deviation, myocardial infarction, ST Segment/T waves/U waves), with specific abnormality will be provided in a by subject listing.

Analyses of Vital Sign Variables

The summary statistics of all vital sign variables (vital signs values and changes from baseline) will be calculated for each visit. Summary tables will be provided for all treatment visits, both chronic and flare-up visits. For these tables, the baseline value for the MOVE trial is the last available value prior to or on the date of first dose of chronic treatment. For the NHS study, the baseline value is the value taken at the Day 1 visit. Summary tables will also be provided for flare-up treatment visits only using date of flare-up dosing to derive change from baseline. For flare-up treatment, subjects may contribute more than one observation for summaries due to multiple cycles of flare-up treatment. Each cycle of flare-up treatment will be summarized separately. For these tables, the baseline value for the MOVE trial is the last available value prior to or on the date of first dose of flare-up treatment within the cycle. For the NHS study, the baseline value is taken at Day 1 of each individual flare-up.

The incidence of PCSs at any time (see [Appendix 6.2](#) for the PCS list) during the treatment period will be summarized in the same manner as lab PCS tables.

All PCS values will be presented in a separate listing as well.

Analyses of C-SSRS Variables

The palovarotene treated and NHS untreated subjects who report any type of suicidal ideations in the Columbia-Suicide Severity Rating Scale (C-SSRS) or any suicidal behavior during the study will be presented in listings.

A tabular summary of subjects with any type of suicidal ideation or behavior will be presented.

A listing will summarize any subject with Type 4 or 5 suicidal ideation or any suicidal behavior.

Analysis of Hearing Assessments

Hearing was assessed via age-specific pure tone audiogram monitoring via baseline and follow-up age-specific hearing evaluation tests. A listing will summarize by-subject results.

Pregnancy and Teratogenicity Assessment

Pregnancy and pregnancy outcomes were monitored throughout the study. A listing will summarize by-subject results.

Bone Safety Assessments

Two events led to a prolonged treatment interruption period. The first interruption occurred following a partial clinical hold issued by the US Food and Drug Administration (FDA) on the 4 December 2019 for subjects under 14 years of age in palovarotene clinical studies due to the identification of the risk of PPC. The second interruption occurred following the outcome of the PVO-1A-301 second interim analysis that crossed the threshold for futility, which resulted in the per-protocol treatment discontinuation of subjects ≥ 14 years of age on 24 January 2020.

Bone safety data will be described for following time periods:

The Original Baseline Period

The original baseline period will be defined by the original baseline through February 2020.

The Interruption (Off-treatment) Period

The baseline for the off-treatment period is the earlier of the first assessment while off-treatment or the assessment within 1 month prior to the last dose of palovarotene. Bone growth assessments during the interruption period included subjects in the off-treatment population, which was defined as subjects < 18 years of age at first study entry who interrupted palovarotene after the clinical hold date and did not re-initiate treatment and who had an off-treatment baseline and post-off-treatment baseline visit.

The end of the interruption period occurred either at the end-of-treatment/end of study visit if the subject discontinued from the study, at the end-of-study visit if they completed the study, at the new baseline if the subject re-initiated palovarotene treatment.

The New Baseline Period

A new baseline was established by the re-initiation of palovarotene dosing following the interruption period. New baseline bone growth assessments includes all subjects who had a new baseline and a post-new baseline visit and received at least one dose of palovarotene after the new baseline visit date. The new baseline visit date was defined as the date of the last visit prior to the re-initiation of palovarotene treatment following the interruption period.

Note that bone safety analysis will also be performed based on premature physal closure status.

Analyses of Knee and Hand/Wrist Radiographs and WBCTs for Assessment of Bilateral Hand/Wrist and Knee Epiphyseal Growth Plate

The summary statistics of bone age and the difference between bone age and chronological age (ratio of change from baseline in bone age to change from baseline in chronological age) will be calculated for each visit.

Figures will include a by-subject spaghetti plot of the bone age by chronological age, and a summary figure by sex and age group (4-10, 11-18) with femur length and tibia length on the y-axis and visit on the x-axis. Similar figures will be produced using chronological age in place of bone age.

Summary tables of growth plate abnormalities identified in radiographs (MOVE Trial only) will include the following:

- Number and proportion of subjects with any abnormality at baseline, and by specific abnormality (e.g., growth recovery lines, sclerosis, etc.)
- Number and proportion of subjects with any new post-baseline or prior time point abnormality, and by specific abnormality
- Number and proportion of subjects with any new post-baseline or prior time point worsening, and by specific abnormality
- Number and proportion of subjects with improvement from baseline or prior time point abnormality, and by specific abnormality

Summary tables of growth plate abnormalities identified in WBCT safety reads (MOVE Trial and NHS) will include the following:

- Number and proportion of subjects with any abnormality at baseline, and by specific abnormality (e.g., growth recovery lines, sclerosis, etc.)
- Number and proportion of subjects with any new post-baseline or prior time point abnormality, and by specific abnormality
- Number and proportion of subjects with any new post-baseline or prior time point worsening, and by specific abnormality
- Number and proportion of subjects with improvement in baseline or prior time point abnormality, and by specific abnormality

Listings of all subjects with premature growth plate closure will be provided.

Bone Age

Bone age is assessed by hand/wrist radiographs. To normalize change in bone age over time, the ratio of change from baseline in bone age to change from baseline in chronological age will be calculated such that a ratio of 1 indicates the same progression over time, while a ratio >1 indicates faster progression of bone age relative to chronological age. Descriptive statistics will be analyzed by timepoint.

Bone age will also be assessed by age category and premature physal closure (PPC) status.

Analyses of Knee Alignment

Summary statistics of lateral distal femoral angles will be calculated for each visit and new-onset potentially clinically significant knee lateral distal femoral angles (i.e. angles outside of the physiological range defined as 78.9 to 84.9 degrees). Listings will also be generated for subjects meeting PCS criteria overall and by PPC status.

Analyses of Standardized Stadiometry and Knee Height for Assessments of Linear Growth

The summary statistics of linear height for age z-score and knee height (values and changes from baseline) will be calculated for each visit. Figures will include height z-scores over time and knee height over time. In addition, summary statistics of weight for age z-score and BMI (kg/m^2) for age z-score (values and changes from baseline) will be calculated for each visit and plotted against age.

The z-scores will be calculated by using US Centers for Disease Control and Prevention (CDC) growth charts, using the SAS macro from <http://www.who.int/childgrowth/software/en/>. (Note that the derivation of the z-scores depends on sex and age in months.)

Growth velocity will also be summarized in tables and figures. The calculation of growth velocity will be performed as follows: $((\text{Current Height} - \text{Previous Height}) / (\text{duration (days)} = (\text{current date} - \text{previous date}))) * 365.25 = \text{Annualized Growth Velocity (cm/year)}$. In addition to providing the calculated growth velocities per time period for each subject, the data will also be categorized according to worst growth velocity and last growth velocity by the following three categories: <4 cm/year; 4 to 5 cm/year; and >5 cm/year.

Growth assessments (linear height, knee height, and femur and tibia lengths and growth velocity over 12 months) will also be assessed by age category, treatment status and premature physeal closure (PPC) status.

Analyses of WBCT Measurements of Femur and Tibia Lengths The summary statistics of femur and tibia lengths (values and changes from baseline) will be calculated for each visit. Femur and tibia lengths will be summarized for the following subgroups:

- Male, Age 4-10 years
- Male, Age 11-18 years
- Female, Age 4-10 years
- Female, Age 11-18 years
- Female Age ≤ 8 , Male Age ≤ 10 years
- Female Age >8 to <14, Male Age >10 to <14 years
- Age ≥ 14 years

Figures will include spaghetti plots of the femur and tibia change from baseline by chronological age.

Leg Length Discrepancies

Leg length discrepancies will be calculated by the difference in right and left femur and tibia lengths as measured by low-dose WBCT. Potential clinically meaningful leg length differences

(ie, >1.5 cm difference) were compared with untreated NHS subjects by age category and PPC status.

Analyses of Evaluation of Bilateral Hips by WBCT Safety Read

Summary tables of hip abnormalities identified in WBCT safety reads (MOVE Trial and NHS) will include the following:

- Number and proportion of subjects with possible, probable, or definite avascular necrosis (AVN) at baseline, and by specific abnormality (e.g., subchondral lucency, osteosclerosis, etc.)
- Number and proportion of subjects with any new post-baseline or prior time point AVN, and by specific abnormality
- Number and proportion of subjects with any new post-baseline or prior time point worsening in AVN, and by specific abnormality
- Number and proportion of subjects with improvement in baseline or prior time point AVN, and by specific abnormality

Assessments for Spinal Health

WBCT scan assessments described above, will also be used to analyze spinal bone mineral density, bone strength, bone mineral content and fractures, utilizing biomechanical computed tomography (BCT) analysis. These results will be compared to NHS subjects (Study PVO-1A-001). To assess potential effect of palovarotene on these parameters modeling will be performed at month 12 with comparison to NHS subjects. Additionally descriptive statistics will be provided for each timepoint.

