### **7.2.8 Adverse Events**

Adverse event monitoring will be conducted throughout the study for all subjects. The AE, SAE and death reporting period begins at the time of informed consent and continues through Part A/B EOS +30 days (for subjects not participating in Part C) or Part C SC + 30 days.

The Investigator will follow-up on all AEs observed or reported by the subject up to the end of the reporting period or until follow-up is no longer necessary. The Investigator will follow-up on SAEs until they are considered resolved or the outcome is known. Limb/joint AEs reported by subjects with open epiphyses will be evaluated by clinical and radiographic assessments deemed appropriate by the Investigator.

Definitions, documentation, and reporting of AEs are described in Section 9.1. Serious adverse events must be reported within 24 hours as described in Section 9.1.8.

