2.1.4 Safety Endpoints

Safety evaluations will include adverse event (AE) and serious AE (SAE) reporting, electrocardiograms, vital signs (temperature, respiratory rate, blood pressure, and heart rate),

physical examination, body weight/BMI, knee and linear height, laboratory parameters (hematology, biochemistry, and urinalysis), urine pregnancy tests for FOCBP, radiographic imaging and whole body computed tomography (WBCT), concomitant medication reporting, and the age-appropriate C-SSRS.

Adverse Event Variables

Adverse Event Observation Periods

- A Pre-treatment AE is an AE with an onset date before the first dose of study drug.
- TEAEs are AEs with (first dose date of study drug) \leq (AE start date) \leq (last dose date of study drug +7 days for all AEs, i.e., non-serious and serious AEs).
 - A chronic TEAE is a TEAE with an onset date during chronic treatment
 - A flare-up TEAE is a TEAE with an onset date during flare-up treatment
- Post-treatment AEs are AEs with a start date $>$ last dose date + 7 days for All AEs (non-serious and serious AEs).

Note that subjects may have multiple independent flare-up treatment cycles, each potentially with associated AEs, within the study.

For the efficacy interim analysis and final analysis, treatment emergence for chronic or flare-up treatment is determined based on the subject's dosing diary. For all other pre-lock analyses, treatment emergence is determined using the subject's planned dosing log if insufficient diary data is available, with the date of the extract of data for the interim analysis used as the end date for TEAE assignment purposes.

Any AE with a missing start date is considered TEAE. For TEAEs that have a partial date where the day is missing, if the month is the same month as a flare-up treatment was given, then the TEAE will be defined as a TEAE associated with flare-up dosing.

All AEs (including SAEs) will be coded using a current or recent version of MedDRA. Adverse event severity will be assessed and reported according to criteria defined in the protocol (mild, moderate, severe). Adverse event causality will also be assessed in terms of relationship to study drug and reported according to criteria described in the protocol (not related, possibly related, probably related, definitely related).

The occurrence of AEs (including SAEs) will be recorded from the time of signed informed consent until the end of the study.

Deaths

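### SAP 2.4.5 and 2.1.4 conflict for adverse events with a missing start day: 2.4.5 classes them as treatment-emergent without checking last dose, so off-drug events could be counted as on-drug

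*SAP*

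**What the plan says.** SAP 2.1.4 (Adverse Event Observation Periods) defines a treatment-emergent AE as one starting between first dose and "last dose date of study drug +7 days for all AEs, i.e., non-serious and serious AEs". Anything later is post-treatment. On partial dates it adds one thing. For an event that has no start day but is already taken to be treatment-emergent, it says: "if the month is the same month as a flare-up treatment was given, then the TEAE will be defined as a TEAE associated with flare-up". Such an event therefore goes to the flare-up column.

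SAP 2.4.5 (General Rules) sets the conventions for partial and missing AE dates. For a missing day it has three branches, tested in order:

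1. If the month falls within flare-up treatment, the flare-up treatment date is used, "and the AE is considered treatment emergent and assigned to the flare-up dosing period".
2. Otherwise, if the month is on or after first dose, the rule reads: "the start date is imputed as the date of first dose or the first day of the month of the AE, whichever is later". It classes the AE as treatment-emergent and places it under chronic dosing.
3. Otherwise, if the month is before that of first dose, the first of the month is used and the AE is not treatment-emergent.

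When day and month are both missing, 2.4.5 covers only a start year equal to, or earlier than, the year of first dose.

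The AE tables have columns for chronic dosing, flare-up dosing and overall palovarotene. Pre-treatment and post-treatment AEs are reported separately (SAP 2.4.5, Analyses of Adverse Events). Part C involves no dosing and runs for up to 2 years after last dose (SAP 1.5). AE collection "continues through Part A/B EOS +30 days (for subjects not participating in Part C) or Part C SC + 30 days" (Protocol 7.2.8).

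**The concern.** Branch 2 assigns a class as well as a date, and it has a lower limit but no upper one. An AE whose recorded month lies entirely after the 7-day window is known to be off drug, yet the branch calls it treatment-emergent. The same event with a full date would be post-treatment.

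This goes beyond conservative imputation. Calling an event treatment-emergent is defensible when the partial date leaves the matter open. Here the month settles it, and branch 3 already uses that reasoning before first dose. There is no matching branch after last dose.

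What is at stake is the separation of on-drug from off-drug safety. Subjects under 14 stopped drug on 4 December 2019 and were not restarted (SAP 1.5), and off-treatment safety in skeletally immature subjects is the stated objective of Part C. The scheduled Part C visits are widely spaced: Year 1 at 6 to under 18 months after last dose and Year 2 at 18 to 24 months (Protocol Table 3). A day-missing event from that period would leave the post-treatment tables and enter the chronic-dosing and overall columns.

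**Working it through.** The plan has no figure to reproduce here. The check is to run the two rules on the same records.

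**Inputs.** The rules are those of SAP 2.4.5 and 2.1.4. The subject is illustrative: first dose 15 January 2018; one flare-up cycle from 10 June to 1 September 2018; last dose 4 December 2019, the date of the clinical hold. The 2.1.4 window then closes on 4 + 7 = 11 December 2019.

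**Step 1: impute and class under 2.4.5, then test the imputed date against the 2.1.4 window.** (TE = treatment-emergent.)

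| Recorded start | Imputed date | Days from last dose | Class under 2.4.5 | Class under 2.1.4 |
|---|---|---|---|---|
| Dec 2017 | 1 Dec 2017 | −733 | not TE | pre-treatment |
| Jan 2018 | 15 Jan 2018 | −688 | TE, chronic | TE |
| Jun 2018 | 10 Jun 2018 | −542 | TE, flare-up | TE |
| Nov 2019 | 1 Nov 2019 | −33 | TE, chronic | TE |
| Dec 2019 | 1 Dec 2019 | −3 | TE, chronic | TE |
| Jan 2020 | 1 Jan 2020 | 28 | TE, chronic | post-treatment |
| Nov 2020 | 1 Nov 2020 | 333 | TE, chronic | post-treatment |
| Mar 2021 | 1 Mar 2021 | 453 | TE, chronic | post-treatment |
| Nov 2021 | 1 Nov 2021 | 698 | TE, chronic | post-treatment |

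For March 2021: 4 December 2019 to 4 December 2020 is 366 days (leap year), and from there to 1 March 2021 is 27 + 31 + 28 + 1 = 87 days. The total is 366 + 87 = 453, against an allowance of 7.

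**Step 2: where the rules part.** They agree up to and including the month of last dose. From January 2020 to December 2021, which is 12 + 12 = 24 calendar months and reaches 2 years after last dose, they disagree in every month.

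**Step 3: the flare-up branch.** It does not cause the problem. A month in which flare-up treatment was given cannot lie wholly after last dose.

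**Step 4: effect of applying 2.1.4 after imputation.** Branch 2 imputes the first of the month (or first dose, if later). The imputed date is therefore beyond last dose + 7 days exactly when the whole month is. In the table, January 2020 and the later rows become post-treatment. November and December 2019 stay treatment-emergent, and June 2018 stays with flare-up dosing.

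**Step 5: year-only dates.** For the same subject, an AE dated only 2018 is imputed to first dose and one dated 2017 to 1 January 2017. An AE dated only 2019 or 2020 meets no condition in 2.4.5 and receives neither a date nor a class.

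**The case against.** The strongest reply is that the SAP does have an upper limit. SAP 2.1.4 states it for all AEs, and 2.4.5 presents its rules as imputation conventions, so a programmer could reasonably impute under 2.4.5 and then classify under 2.1.4. That would give the right answer. This stands to the extent that misclassification is not certain. It does not remove the conflict, because 2.4.5 also dictates the class and nothing ranks one section above the other.

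A reader might infer that Part C events generally are tabulated as on-drug. The documents do not support that. Fully dated Part C events are post-treatment under 2.1.4. Only events with a missing start day are exposed, and only if 2.4.5 is taken to override. A mislabelled event would also remain traceable: there is a Part C Analysis Set (SAP 2.3), a Part C safety summary (Protocol 8.5.3) and AE listings (SAP 2.4.5).

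A reader might also turn an assumed rate of missing days into an equal percentage shortfall in post-treatment counts. That does not follow. The tables count subjects, and repeats of the same event in a subject count once. A subject with another, fully dated occurrence of the same event after treatment stays in that post-treatment row. One who already had the event during chronic dosing adds nothing to the chronic column.

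Nor do the documents show that missing days are common. Part C collects AEs at every contact (Protocol Table 3), onset date is part of each AE report (Protocol 9.1.3), and SAEs are reported within 24 hours (Protocol 9.1.8). All of this limits the size of the problem but leaves the conflict in place.

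**Conclusion.** The point holds as a conflict between two stated rules. For a day-missing AE in a month wholly later than last dose + 7 days, SAP 2.4.5 gives treatment-emergent with chronic dosing, and SAP 2.1.4 gives post-treatment. Followed literally, 2.4.5 gives a wrong result for an event that its recorded month already places off drug.

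The size cannot be computed. The affected records range from none to all day-missing post-treatment AEs, and the effect on the tables may be smaller still because they count subjects. The worked example assumes illustrative dates and takes last dose to be the subject's final dose. Confidence is high that the wording conflicts. Whether any event has been or will be misclassified depends on how the program was written and on how many partial dates exist, neither of which the documents show.

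The missing year-only rule is a separate and smaller gap. It is an omission, so it is not evidence that such events are put in the wrong column.

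**What to change.** Amend SAP 2.4.5 as follows:

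- **Missing day.** State that the 2.1.4 window is applied after imputation. An AE whose recorded month is wholly later than last dose + 7 days is post-treatment. A month overlapping the treatment period or the 7-day window stays treatment-emergent, which keeps the conservative choice where the date leaves doubt.
- **Year only, after the year of first dose.** Class the AE as post-treatment only if the whole year is later than last dose + 7 days, and otherwise as treatment-emergent. Imputing 1 January and applying the same test does this. In the worked example 2019 is treatment-emergent and 2020 is post-treatment.
- **Check.** List the AEs with partial start dates after last dose + 7 days and confirm their class. This also shows whether any record is affected.

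The cost is a few sentences and one programming check, with no change to endpoints or data collection. There is one small downside. SAP 3.3 says analyses in the interim CSR are not planned to be rerun for the final CSR, so interim and final safety tables could rest on different date rules. The final CSR should note the change.
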